## 5.6 Treatment Regimen and Dosing

### 5.6.1 Study Treatments

BOTOX

#### Study Treatment 1

All eligible patients who meet inclusion/exclusion criteria and are enrolled into the study will receive a double-blind treatment of either BOTOX 100 U or placebo for their first study treatment.

The first treatment will be administered after randomization on Day 1 at the investigational site. All Day of Treatment Criteria must be fulfilled prior to treatment administration (see [Section 5.9.1 Day of Treatment 1 Criteria](#)).

#### Study Treatment 2

All patients can request and potentially qualify for a second treatment, and if the qualification criteria are met (Qualification for Treatment 2 Criteria provided in [Section 5.10.1 Request/Qualification for Treatment 2](#)) they will receive BOTOX 100 U for their second treatment.

Administration of Treatment 2 should occur within 28 days of the qualification for Treatment 2 visit. Patients must fulfill the ‘Day of Treatment 2 Criteria’ prior to Treatment 2 administration (see [Section 5.10.2 Day of Treatment 2 Criteria](#)). Treatment 2 must not be administered before 12 weeks after Treatment 1.

The reason(s) for the patient requesting retreatment will be collected at each visit in which the request is made, regardless of whether the patient qualifies for Treatment 2 at that visit or not.

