### 7.2 Collection and Derivation of Primary and Secondary Efficacy Assessments

#### 7.2.1 Primary Efficacy Variables

The primary efficacy endpoint is:

- Change from baseline in number of episodes of urinary incontinence at Week 12 as recorded by the patient in the 3-day bladder diary.

The following algorithms will be used for diary data conventions:

If there are no diary data (ie, none of the 3 diary days is a valid diary day), then the daily average frequency of urinary incontinence episodes will be considered as missing.

If a diary is completed for at least 1 day at any particular visit, then that patient's daily average frequency of urinary incontinence episodes in a 3-day period for that given visit will be estimated by using the daily average number of urinary incontinence episodes of the available days in the 3-day diary period.

A valid diary day is defined as a day in any of the three 24-hour periods with 2 or more urinary episodes of any type. For a valid diary day, if no incontinence episodes are recorded, the number of incontinence episodes on that day will be treated as zero. For an invalid diary day, both the number of incontinence episodes on that day will be treated as missing.

If the number of episodes of urinary incontinence at baseline is missing, it will be imputed using the median of all non-missing values regardless of treatment group at study baseline.

[figure not shown]
For each scheduled post-treatment visit, missing values for the primary efficacy variable will be imputed using the last observation carried forward (LOCF) approach. Additional details will be provided in the SAP.

[figure not shown]

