## 7.6 Primary Analysis

A primary analysis will occur when all patients have completed 12 weeks following Treatment 1 (double-blind period) or early terminated. Only tables will be produced (no patient listings will be produced), thus maintaining patient and site/investigator treatment blinding. The primary analysis (topline data) will be a subset of the final analyses performed for the final CSR. Analyses included in the primary analysis will be flagged in the SAP list of table, figure, and listing mocks.

The main purpose of the primary analysis is for presentation of the key data as soon as possible at an international urological or urogynecological conference to ensure dissemination of results in a timely manner. The topline primary analysis data will include key efficacy and safety analysis from the first 12 weeks after treatment 1 (double-blind data).

For the purpose of the primary analysis, statistics and programming staff from the vendor CRO, will have blinded and unblinded teams set up for the analysis, per details contained in the SAP and/or other documentation listing those who will be unblinded. Unblinded statistical team will work in a restricted secure study location.

Only Allergan study team members and corresponding co-authors will receive the topline primary analysis data (no analysis datasets and listings will be distributed, therefore the Allergan team and co-authors will not be unblinded to patient level data). Those who will be unblinded in Allergan will be listed in an other document. No CSR will be authored following the primary analysis.

[figure not shown]
Full unblinding will occur following the final database lock at the end of the study, for the final CSR.

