2.3.1.1 Handling of Missing Data for Primary Efficacy Variables

The primary efficacy endpoint is:

- Change from baseline in number of episodes of urinary incontinence at Week 12 as recorded by the subject in the 3-day bladder diary.

The following algorithms will be used for diary data conventions:

If there is no diary data (i.e., none of the 3 diary days is a valid diary day), the daily average frequency of urinary incontinence episodes will be considered as missing. A valid diary day is defined as any of the three 24-hour periods with 2 or more urinary episodes of any type. For a valid diary day, if no incontinence episodes are recorded, the number of incontinence episodes on that day will be summarized as zero. For an invalid diary day, the numbers incontinence episodes on that day will be treated as missing.

If a diary is completed for at least 1 day of diary at any particular visit, then that subject's daily average frequency of urinary incontinence episodes in a 3-day period for that given visit will be estimated by using the daily average number of urinary incontinence episodes of the available days in the 3-day diary period.

If the number of episodes of urinary incontinence at study baseline is missing, it will be imputed using the median of all non-missing values regardless of treatment group at study baseline. For each scheduled post treatment visit within the 12-week period of the DB treatment period, missing values for the efficacy variable (the change from baseline in the daily frequency of episodes of urinary incontinence) will be replaced using the last observation carried forward approach. If subjects requested and received a second treatment on or after Week 12, they are no longer in DB treatment period and the LOCF rule for DB treatment period should no longer apply to them. The LOCF rule will be applied to subjects without a second treatment of BOTOX® through 36 weeks for endpoints where data are analyzed to the end of the study.

When implemented, imputation of missing values will be performed only for subjects who receive a treatment in the pertinent treatment period. For example, only subjects receiving a second treatment will have values imputed in OL treatment period; subjects who discontinued from the study during the first treatment will not have data imputed for OL treatment period.

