3.2 Disposition and Exit Status

The number and percentage of subjects in each analysis population will be summarized by treatment group and overall. For the subjects who discontinued early, the primary reason for discontinuation will be summarized. Duration in DB and OL period will be calculated as below and will be summarized:

- For subjects were not re-treated, duration in DB period will be calculated as (date of discontinuation/completion – date of initiation of DB treatment + 1).
- For subjects were re-treated, duration in DB period will be calculated as (date of initiation of OL treatment – date of initiation of DB treatment + 1); duration in OL period will be calculated as (date of discontinuation/completion – date of initiation of OL treatment + 1);

Study day of discontinuation will be calculated as below and listed.

- For subjects that terminate the study early and were not re-treated, study day of discontinuation will be calculated as (date of discontinuation – date of initiation of DB treatment + 1).
- For subjects that terminate the study early and were re-treated, study day of discontinuation will be calculated as (date of discontinuation – date of initiation of OL treatment + 1).

Number and percentage of subjects randomized in each country and site will be presented by treatment group and overall.

A data listing for all subjects will display disposition characteristics, including date of initiation of the DB treatment and OL treatment if applicable, study completion status, last study day/date completed, reason(s) for non-completion, date of early termination assessment/study day of termination, and any specific comments related to non-completion.

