6.5 Adverse Events

Treatment-Emergent Adverse Events (TEAEs) are defined as those that begin on or after initiation of first dose of study treatment. For re-treated subjects, the TEAEs started on or after the initiation of DB treatment and before the initiation of OL treatment will be assigned to double-blind period. The TEAEs started on or after the initiation of OL treatment will be assigned to open-label period. Refer to [Table 7](#) for the classification of TEAEs by treatment period as:

- Double-blind period
- Open-label period

Table 7: Classification of TEAEs

Subjects not re-treated:

TEAE Start Date/Time	TEAE Classification
DB Treatment start date/time <= AE start date/time	Double-Blind period

Subjects re-treated:

TEAE Start Date/Time	TEAE Classification
DB Treatment start date/time <= AE start date/time < OL Treatment start date/time	Double-Blind period
AE start date/time >= OL Treatment start date/time	Open-Label period

Adverse events will be classified by type, incidence, severity, and causality. The overall incidence of AEs will be summarized using the MedDRA coding system and classified by SOC, PT, and treatment group.

An overall summary table will present the number of events and the incidence of subjects having at least one event in the following categories:

- TEAEs
- TEAEs indicated as serious (SAEs)
- TEAEs leading to study discontinuation
- TEAEs leading to death
- TEAEs related to study drug
- Serious TEAEs related to study drug
- Possible distant spread of toxin (PDSOT) TEAEs (refer to [Section 6.5.2](#))
- TEAEs of urinary retention (Refer to [Section 6.5.1](#))
- TEAEs of residual urine volume (Refer to [Section 6.5.1](#))
- TEAEs of urinary tract infection (Refer to [Section 6.5.1](#))
 - TEAEs of asymptomatic urinary tract infection
 - TEAEs of symptomatic urinary tract infection

Tabulation (using counts and percentages) of TEAEs classified by SOC and PT will be provided. In addition, Tabulation of TEAEs classified by SOC and PT will be provided for each of the following:

- Serious TEAEs
- Treatment-Related Serious TEAEs
- TEAEs leading to study discontinuation
- Treatment-related TEAEs leading to study discontinuation

Tabulation of TEAEs classified by PT will be provided for each of the following:

- TEAEs
- Serious TEAEs
- TEAEs by maximum severity
 - Subjects with multiple TEAEs with the same PT will be summarized at the maximum severity and counted one time for that PT.
- TEAEs related to study drug

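### Does later retreatment decide whether a missing Week 12 primary value is carried forward?

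*SAP*

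**What the plan says.** Protocol 7.2.1 sets the general rule: "For each scheduled post-treatment visit, missing values for the primary efficacy variable will be imputed using the last observation carried forward (LOCF) approach". It then leaves the detail to the SAP: "Additional details will be provided in the SAP".

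SAP 2.3.1.1 supplies that detail in four steps:

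- LOCF applies at each scheduled visit in the 12-week part of the double-blind period. No exception is stated here.
- "If subjects requested and received a second treatment on or after Week 12", then "they are no longer in DB treatment period and the LOCF rule for DB treatment period should no longer apply to them".
- For endpoints analysed to the end of the study, LOCF runs through 36 weeks in subjects without a second treatment.
- Values are imputed only for subjects treated in the period concerned.

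On timing, Protocol 5.6.1 states "Treatment 2 must not be administered before 12 weeks after Treatment 1". Protocol 7.6 sets the topline cut: "A primary analysis will occur when all patients have completed 12 weeks following Treatment 1 (double-blind period) or early terminated".

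**The concern.** The exception is written by subject and names no visit. Because Treatment 2 cannot precede 12 weeks, it takes in every retreated patient. Suppose two patients have the same data through Week 6 and both miss the Week 12 diary. Taken literally, the one retreated at Week 24 has no primary value, while the other has Week 6 carried forward.

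Three things would then be at stake:

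- Retreatment requires persisting urgency incontinence (Protocol 5.10.1), so it probably differs by arm. A post-Week 12 event related to outcome would decide who enters the Week 12 comparison.
- A value imputed at topline could be missing at the final lock, with no change in the Week 12 data.
- Protocol 7.2.1 has no such exception, yet SAP section 8 reports no change from the protocol.

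A related worry comes from Protocol 5.10.1, under which a visit where a requester is assessed stops counting as the post-treatment visit. A patient who qualifies at Week 12 might then seem to have neither an observed nor a carried-forward value.

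**Working it through.** **Reading the text**

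1. *The 12-week sentence.* It grants LOCF at every visit in that window. A patient retreated at Week 24 was in the window at Week 12.
2. *When the double-blind period ends.* SAP 3.2 counts it up to open-label treatment: "For subjects were re-treated, duration in DB period will be calculated as (date of initiation of OL treatment" minus the double-blind start date, plus one). SAP 6.5 agrees: events that "started on or after the initiation of DB treatment and before the initiation of OL treatment will be assigned to double-blind period". So a patient retreated at Week 24 was still in the double-blind period at Week 12, and the phrase *no longer* is untrue of that visit. It becomes true at Treatment 2.
3. *The treatment-period sentence.* It makes imputation depend on having been treated in the relevant period. Every retreated patient was treated in the double-blind period, so this condition does not bar Week 12 imputation.
4. *The end-of-study sentence.* It limits LOCF through 36 weeks to patients without a second treatment. The exception leads into it and explains why a pre-retreatment value is not carried past retreatment.
5. *The analysis population.* Protocol 7.3.1 bases the primary analysis on the mITT Population with imputation. The literal reading would leave some mITT patients with a valid earlier diary and no Week 12 value.
6. *Patients who qualify at Week 12.* Qualifying requires three consecutive diary days in the week before the visit (Protocol 5.10.1). These patients should have an observed diary and need no LOCF. The relabelling clause goes on to say which eCRFs to complete, so it reads as a data-entry instruction.

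**Size if the literal reading were applied**

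Inputs from Protocol 7.5: mean changes -2.8 (SD 3.45) and -0.95 (SD 2.9), 68 and 34 patients, two-sided 5% z-test, 10% dropout.

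The plan's own figures reproduce:

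- SE = √(3.45²/68 + 2.9²/34) = 0.650
- Power = Φ(1.85/0.650 − 1.96) = 81.2%, against a stated 80%
- 102/0.9 = 113.3, rounded up to 114, which is 76/38 at 2:1. Power at 76/38 is 85.3%.

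The documents give no missed-diary or retreatment rate, so both are assumed. Let m be the share missing the Week 12 diary and r the share of those later retreated. Patients losing a value = 114 × m × r. Power is recalculated with each arm reduced by the factor (1 − m × r).

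| m | r | Patients of 114 | Power from 76/38 | Power from 68/34 |
|---|---|---|---|---|
| none | – | 0 | 85.3% | 81.2% |
| 2% | 25% | 0.6 | 85.1% | 81.0% |
| 5% | 50% | 2.9 | 84.4% | 80.3% |
| 10% | 75% | 8.6 | 82.5% | 78.2% |

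*Effect on the estimate.* Suppose 30% on BOTOX and 70% on placebo are retreated, and the affected patients are D episodes per day worse than the rest of their arm. Dropping them moves the difference toward zero by D × m × (0.70 − 0.30).

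- Smallest case: 1 × 0.02 × 0.40 = 0.008
- Largest case: 3 × 0.10 × 0.40 = 0.12, against a planned difference of 1.85

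*Topline against final.* Treatment 2 may be given up to Week 34 plus 7 days, that is Week 35. With even accrual over 24 months (104 weeks), (35 − 12)/104 = 22% of patients, about 25 of 114, are 12 to 35 weeks past Treatment 1 at the cut. Multiplying by m × r (0.5% to 7.5%) gives 0.1 to 1.9 patients whose value could change. With accrual over 12 months the share is 23/52 = 44%, about 50 patients, giving 0.3 to 3.8.

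**The case for a change.** The strongest counter-argument is redundancy. If the exception starts only at Treatment 2, it takes nothing from the 12-week sentence, because Treatment 2 cannot come earlier. For later visits, the end-of-study sentence already leaves retreated patients out. A programmer who assumes that each sentence must do separate work arrives at the literal reading. The treatment-period sentence does not rule this out, since it states a necessary condition and does not restore what another sentence removed. No sentence says outright that values due before Treatment 2 stay imputable.

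The missing time limit stands as a fact. The inference from redundancy is weak: a sentence that introduces the next one is common in an SAP, and the literal reading needs the double-blind period to mean something different from SAP 3.2 and 6.5. The end-of-study sentence is also written by subject, so a patient who misses Week 24 and is retreated after Week 30 might get no Week 24 value. That concerns later visits, not the primary endpoint.

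The charge of departing from the protocol does not stand. Protocol 7.2.1 hands the details to the SAP, and on the temporal reading SAP section 8 is accurate on this point. Nor can it be said that no visit-mapping rule exists for patients who qualify at Week 12: the visit schedule and parts of the SAP are blacked out.

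**Conclusion.** No change follows. The wording leaves a gap that analysts can fill from the SAP itself: a patient retreated after Week 12 was in the double-blind period at Week 12 and keeps the carried-forward value, and the exclusion applies from Treatment 2 onward. On that reading, Week 12 imputation does not depend on retreatment, topline and final results agree on this point, and stating the time limit would alter no result.

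Even the literal reading has a limited reach. A diary counts as missing only when none of its three days is valid. Under the assumed rates, the loss is about 1 to 9 of 114 patients and at most about 3 points of power. With the further assumptions on retreatment by arm and on outcome, the treatment difference shrinks by at most 0.12 episodes per day. These sizes rest on rates that the documents do not give. The conclusion itself rests on how the SAP defines the double-blind period.

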2.3.1.2 Handling of Missing Data for Secondary Efficacy Variables

[figure not shown]
There are 5 secondary efficacy variables as follows:

- Proportion of subjects who achieve 100% reduction in urinary incontinence episodes (complete continence) from baseline (i.e., baseline prior to DB treatment).
- Change from baseline in daily average number of micturition episodes.

- Change from baseline in daily average number of urgency episodes
- Change from baseline in daily average number of nocturia episodes.
- Proportion of subjects who have a positive treatment response on the Treatment Benefit Scale (TBS) (score of either 1 or 2, representing 'greatly improved' or 'improved', respectively) at Week 12.

The derivation of the first 4 secondary endpoints above, recorded from the 3-day bladder diary at each visit, will follow the same data convention and imputation approach as for the primary efficacy endpoint described in [Section 2.3.1.1](#).

Missing values for TBS will not be imputed.

2.3.2 Handling of Missing Date

As a general principle, imputation of missing dates for variables will not be done. Exceptions are for start and stop dates of AEs and concomitant medications. Listings of the AEs and concomitant medications will present the actual partial dates; imputed dates will not be shown.

The following conventions will be used for missing adverse event dates and prior and concomitant dates.

2.3.2.1 Adverse Events Onset Date

If the AE onset date is missing in which the day, month, and year are all unknown or only the day is known, the AE onset date is set to the date of initiation of the DB treatment.

For the partial AE onset date and time,

- If the year is present and the month and day are missing or the year and day are present and the month is missing:
 - If year = year of initiation of DB treatment, then set month and day to month and day of initiation of DB treatment
 - If year < year of initiation of DB treatment, then set month and day to December 31st.
 - If year > year of initiation of DB treatment, then set month and day to January 1st.
- If the month and year are present and the day is missing:
 - If year = year of initiation of DB treatment and:
 - if month = month of initiation of DB treatment then set day to day of initiation of DB treatment
 - if month < month of initiation of DB treatment then set day to last day of month
 - if month > month of initiation of DB treatment then set day to 1st day of month
 - If year < year of initiation of DB treatment then set day to last day of month
 - If year > year of initiation of DB treatment then set day to 1st day of month
- If the imputed AE onset date is after AE stop date, then set the onset date to the AE stop date.

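### Incomplete AE onset dates are imputed without reference to open-label treatment, so some events after Treatment 2 are counted as double-blind, in both arms

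*SAP*

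**What the plan says.** SAP 2.3.2 generally rules out imputing missing dates, but AE dates are excepted: "Exceptions are for start and stop dates of AEs and concomitant medications". That exception is specific, so the general statement in SAP 2.3.1 that safety data are not imputed does not switch it off. SAP 2.3.2 adds that in the listings "imputed dates will not be shown".

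SAP 2.3.2.1 gives the AE onset rules. The branches that matter for a retreated subject are:

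- Date fully missing, or only the day known: "the AE onset date is set to the date of initiation of the DB treatment".
- Year known, month missing, same year as the DB start: "If year = year of initiation of DB treatment, then set month and day to month and day of initiation of DB treatment".
- Year known, month missing, later year: "If year > year of initiation of DB treatment, then set month and day to January 1st".
- Month and year known, later month in the DB-start year: "if month > month of initiation of DB treatment then set day to 1st day of month". Months in a later year are treated in the same way.
- Stop-date check: "If the imputed AE onset date is after AE stop date, then set the onset date to the AE stop date".

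None of these mentions the OL treatment date. SAP 6.5 and Table 7 do use it. A retreated subject's treatment-emergent event is double-blind if it starts before the OL injection; otherwise, "The TEAEs started on or after the initiation of OL treatment will be assigned to open-label period".

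Every retreated patient receives BOTOX 100 U, whatever the first treatment was (SAP 1.1.1; protocol Section 3). Double-blind summaries are shown as BOTOX 100 U and Placebo (SAP 2.3).

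**The concern.** The imputed date feeds a classification that depends on the OL injection date, yet the imputation ignores that date. An event that began after open-label BOTOX can be given an onset before the injection and then be tabulated under the patient's double-blind arm. In a placebo patient, that puts a BOTOX-exposed event in the placebo column.

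The double-blind AE tables are the trial's only placebo-controlled safety comparison, and protocol Section 2.2 makes the safety profile one of the clinical hypotheses. Fully missing dates, and year-only dates in the DB-start year, are set to the day of first treatment. That lies inside the 12-week window of the topline analysis (SAP Section 7). Because imputed dates are not listed, a reader of the listings would not see the reassignment.

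**Working it through.** The documents give no figure for this, so the check is on the date logic.

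**Worked dates**, applying SAP 2.3.2.1 and then Table 7, with no stop date known:

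| DB start | OL start | True onset | Known | Imputed onset | Period |
|---|---|---|---|---|---|
| 15 Mar 2017 | 10 Jun 2017 | 20 Jun 2017 | nothing | 15 Mar 2017 | DB, wrong |
| 15 Mar 2017 | 10 Jun 2017 | 20 Jun 2017 | year | 15 Mar 2017 | DB, wrong |
| 15 Mar 2017 | 10 Jun 2017 | 20 Jun 2017 | month, year | 1 Jun 2017 | DB, wrong |
| 15 Mar 2017 | 10 Jun 2017 | 20 Jul 2017 | month, year | 1 Jul 2017 | OL, right |
| 15 Sep 2017 | 10 Jan 2018 | 20 Feb 2018 | year | 1 Jan 2018 | DB, wrong |
| 15 Sep 2017 | 20 Dec 2017 | 20 Jan 2018 | year | 1 Jan 2018 | OL, right |

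**Direction.** For a true double-blind event, each branch returns the DB start, a date before it, or the first day of the onset month or year. All of these precede the OL injection. The stop-date check can only move an onset earlier. So no double-blind event can become open-label, and the error runs one way.

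**How often the rule fails.** This is a simulation of 50,000 events per scenario. Its assumptions are not in the documents: DB start uniform over a calendar year, OL injection uniform over Weeks 12 to 34, onset uniform over the stated interval after the injection, and no stop date.

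| Missing | Onset 0–84 days after OL | Onset 0–14 days after OL |
|---|---|---|
| whole date | 100% put in DB | 100% |
| all but year | 88% | 98% |
| day only | 17% | 74% |

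Results are almost the same with OL at Weeks 12–16 or 30–34.

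The day-only row can be checked by hand. Take a 30-day month with the injection equally likely on day d = 1 to 30. The rule fails for d = 2 to 30 when onset falls in the remaining 31 − d days of the month, counting the injection day.

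- 0–84 days (85 possible days): (29 + 28 + … + 1)/30 = 435/30 = 14.5, and 14.5/85 = 17%.
- 0–14 days (15 possible days): (15 × 15 + 14 + 13 + … + 1)/30 = (225 + 105)/30 = 11, and 11/15 = 73%.

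**Size per patient.** The target of 114 at 2:1 gives 114/3 = 38 placebo and 76 BOTOX patients. One newly counted placebo patient adds 1/38 = 2.6 points; one BOTOX patient adds 1/76 = 1.3 points. If b placebo and a BOTOX patients are newly counted for a term, the BOTOX-minus-placebo difference changes by a/76 − b/38. That is zero when a = 2b, negative when a < 2b and positive when a > 2b. The documents give neither a nor b.

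**The case against.** A reader might infer that the rule biases the safety comparison towards no difference, because BOTOX events leak into the placebo column. The documents do not support that. BOTOX patients may also be retreated, and their second-treatment events move into the BOTOX double-blind column by the same rule. The net effect depends on retreatment rates and on incomplete-date rates by arm, and neither is given.

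A reader might also infer that every partial date after Treatment 2 is misplaced. That is too broad. Day-missing dates in a month after the injection month are classified correctly, as are year-only dates from a year after the injection year.

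The practical reach may be narrow. The events of most interest have measured anchors: urinary retention requires a PVR measurement and CIC, whose start date is documented (protocol 6.3.7.1 and 9.1.2), and UTI requires a culture. These may usually have full dates. A data review precedes hard lock (SAP Section 1), and SAP Section 6 rules out inferential safety comparisons, so no test is affected.

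All of this stands, and it limits the size of the problem. It does not remove the mismatch between SAP 2.3.2.1 and Table 7. SAP Table 6 classifies concomitant medications against the OL start, so the lack of an OL reference for AE onset looks like an oversight.

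**Conclusion.** The rule is wrong as written, but the point is minor. In retreated subjects, SAP 2.3.2.1 places some post-Treatment 2 events in the double-blind period:

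- all those with a fully missing date;
- those with only the year known, when the DB-start or 1 January imputation falls before the OL injection;
- those with only the day missing, when the month is that of an injection given after the 1st.

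Under the stated assumptions, 17% to 74% of day-missing post-OL events are affected, depending on how soon they follow the injection. The shift is from OL to DB only and occurs in both arms, so the net effect on the BOTOX–placebo contrast is unknown.

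The 2.6 points per placebo patient is a ceiling. It applies only if the patient is not already counted for that category, and it takes the placebo arm as 38 from a target of at least 114 randomised. The documents do not give the number of incomplete dates, which is probably small. Parts of the SAP are blacked out, so a correcting rule there cannot be excluded; the visible text of 2.3.2.1, 6.5 and Table 7 has none.

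**What to change.** 1. **Day missing, month and year equal to those of OL initiation (retreated subjects).** Set onset to the OL treatment date, unless the AE stop date is earlier. This mirrors the SAP's own rule for the DB month. The two months cannot coincide, because Treatment 2 comes at least 12 weeks after Treatment 1. Table 7 compares date and time, so say that the imputed onset counts as being at the OL treatment time.
2. **Day missing, later month.** Leave as it is.
3. **Year-only or fully missing dates (retreated subjects).** Assign the period from the visit at which the event was first reported, if that is captured, together with the stop date. Flag events that stay ambiguous and tabulate them both ways.
4. Report how many AE onset dates were imputed in retreated subjects, by arm.

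Replacing the DB start with the OL start throughout would not do. In the same simulation it moved true double-blind events to OL in 100% of fully missing, about 78% of year-only and about 10% of day-missing cases.

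The cost of item 1 is a line of code and one known error: some events from earlier in the injection month, before Treatment 2, will count as open-label. That is the 10% just given. By hand, an average of 14.5 pre-injection days in that month over a DB period uniform from 84 to 238 days gives 14.5 × ln(238/84)/(238 − 84) = 14.5 × 1.041/154 = 9.8%. Stop dates would lower it. Item 3 needs the reporting visit in the data and a short extra table.
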